In Europe, cochlear implantation has become an accepted treatment for patients with UHL. The majority of literature regarding patients with UHL and cochlear implantation involves adults. It has been reported as a viable treatment option in cases of UHL, including sudden sensorineural hearing loss (Firszt et al, 2012), and severe tinnitus (Vermiere & Van de Heyning, 2009; Van de Heyning et al, 2008). Further, cochlear implantation has been shown to offer superior speech perception in noise, sound localization abilities, and subjective perception of hearing quality compared to CROS hearing aids and bone-conduction devices (Arndt et al, 2011).

The practice of providing cochlear implants to children who have significant hearing loss in one ear is of great interest and is occurring with greater frequency as reported in case studies and small set clinical reports (Gantz, et al. 2000, Cadieux et al., 2013; Hassepass, et al., 2013; Plontke et al., 2013; Tzifa and Hanvey, 2013; Távora-Vieirea and Rajan, 2015; Arndt, et al, 2015). Children with severe to profound UHL may have greater potential to benefit from cochlear implantation than adults with UHL from a developmental point of view due to their neural plasticity. They may be more amenable to gaining binaural listening skills after cochlear implantation.

The primary goal of this project is to determine whether children with UHL experience an improvement in speech perception, hearing in noise, localization, and quality of life with a cochlear implant as compared to an unaided listening condition.

2) Objective

The primary purpose of this feasibility study is to demonstrate the effectiveness of cochlear implantation in children with moderate to profound UHL. Postoperative results will be evaluated with:

- i) speech perception measures,
- ii) localization tasks,
- iii) hearing in noise tasks,
- iv) subjective reports.

3) Definitions

Adjusted Constant Error: the rms deviation of the mean responses from the diagonal, computed after compensating for bias. This procedure reduces the bias

when evaluating the relationship between the average response on the azimuth and signal source on the azimuth.

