Programming of the device is completed using the MAX Programming Interface and MAESTRO System Software. The MAESTRO software is used for different intraoperative and postoperative purposes for the MED-EL Cochlear Implant System. It contains the implant Telemetry, Fitting and Configuration of all available audio processors, ART (Auditory nerve Response Telemetry), ESRT (Electrically Evoked Stapedius Reflex Threshold), EABR (Evoked Auditory Brainstem Response) and Audiogram functions. The MAESTRO software is an external component of the MED-EL Cochlear Implant System and is intended to be used in a clinical or office environment by persons adequately skilled and trained to perform all intended tasks and with patients who received one of the intended MED-EL Cochlear implants.

For the pediatric population, the MED-EL Synchrony cochlear implant is currently indicated for children 12 months to 17 years and 11 months of age, who have bilateral sensorineural hearing impairment and obtain limited benefit from appropriately fitted binaural hearing aids. In this study, the use of this system is considered investigational because it will be used for children who have unilateral moderate to profound sensorineural hearing loss rather than bilateral profound sensorineural hearing loss.

5) Study Duration

- a) Enrollment Period
4 years

- b) Study Timeline

Each participant's involvement will last approximately 2.5 years, including: candidacy evaluation, preoperative evaluation, surgical procedure, initial activation of the external speech processor, therapy schedule, and post-initial activation evaluations (3, 6, 9, 12, 18 and 24-months post-initial activation).

- c) Study Endpoint

The study endpoint for each participant is the 24-months post-initial activation interval.

6) Methods

- a) All procedures will be conducted by UNC investigators, including board-certified otologists, audiologists, and speech-language pathologists. Fully informed consent will be obtained from all participants and/or their parents.
- b) Participants must meet the following inclusion criteria and not exhibit any of the exclusion criteria.
 - i) Inclusion Criteria
 - (1) Unilateral moderate-to-profound sensorineural hearing loss.
 - (a) Unaided residual hearing thresholds that yield a PTA at frequencies 500Hz, 1K Hz and 2K Hz of ≥ 70 dB HL in the ear to be implanted. It is possible that subjects may have hearing at other frequencies not included in this average.

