 - (b) Hearing thresholds in the contralateral ear of ≤ 25 dB HL
 - (2) Between 3 years, 6 mos and 6 years, 6 mos of age at implantation.
 - (3) Anatomically normal cochlear nerve
 - (4) Cochlear anatomy that is amenable to cochlear implantation as evaluated by imaging (modality at the physician's discretion) including:
 - (a) Normal cochlear anatomy or

- (b) Incomplete Partition Type II (IP2) with or without Enlarged Vestibular Aqueduct (EVA) or
- (c) EVA with normal partitioning
- (5) No evidence of progressive hearing loss.
- (6) Willing to undergo 4 week hearing aid trial as warranted based on achieving desired audibility when fitted via real ear DSL method. See Reference Appendix B.
- (7) Aided word recognition in the ear to be implanted of 30% or less as measured with CNC words (50-word list)
 - (a) When listening with an appropriately fit hearing aid and masking applied to the contralateral ear (Turner, 2004).
 - (b) Aided testing will be conducted in a sound-proof booth with the participant seated 1 meter from the sound source, facing 0° azimuth. Recorded materials will be presented at 60 dB SPL.
 - (c) The hearing aid output will be measured using DSL targets.
- (8) Realistic parental expectations: *a verbal acknowledgement of the potential benefits and risks, and postoperative variation in performance. For instance, cochlear implantation will not restore normal hearing.*
- (9) Willing to obtain recommended meningitis vaccinations per CDC recommendations.
- (9) Development and cognition within the normal range as measured by the Leiter-R test of nonverbal intelligence and cognitive abilities.
- (10) Parental commitment to study parameters including being able and willing to participate in evaluation schedule, involvement in prescribed therapy, and travel to investigational site and study-related activities.

ii) Exclusion Criteria

- (1) English is not primary language of the home
 - (a) Speech perception materials are presented in English
 - (b) Parental questionnaires are administered in English
- (2) Conductive hearing loss in either ear
- (3) Compromised auditory nerve
- (4) Ossification of the cochlea
- (5) Inability to participate in follow-up procedures (i.e., unwillingness, geographic location)
- (6) History of condition that contraindicates middle or inner ear surgery or anesthesia (i.e. otitis media refractory to treatment)
- (7) Case of sudden sensorineural hearing loss that has not been first evaluated by a physician

iii) Enrollment

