- (1) Speech, Spatial and Qualities of Hearing Scale (SSQ), (Gatehouse & Noble, 2004). The SSQ questionnaire assesses performance in three domains, hearing speech in quiet and noise environments (9 items), spatial or directional hearing (5 items) and sound qualities (8 items), which address sound segregation and listening effort. Each item is rated on a 10-point scale. Domain scores represent an average of item ratings. A modified version of this test will be used.
- (2) Bern SSD Questionnaire, (Kompis, Pfiffner, Krebs & Caversaccio , 2011). This is a 10-item questionnaire used for rating the subjectively perceived benefit of a hearing technology designed to be used for persons with UHL. A modified version of this test that can be completed by a parent will be used.
- (3) PedsQL Multidimensional fatigue scale (Varni, Limbers & Burwinkle, 2007). This is a validated scale for determining fatigue in young children, including general fatigue, sleep/rest fatigue and cognitive fatigue. Scores from this test have been previously demonstrated to be substantially affected by hearing loss in children (Hornsby et al 2013).

e) Aural Rehabilitation

- i) Participants and their parents will participate in aural rehabilitation sessions with a board-certified speech-language pathologist
- ii) Sessions will occur either in person or via tele-therapy at the time of the initial stimulation, 2-week follow up, 5 week follow up, and twice a month following for the first 6 months after the initial stimulation. Sessions will continue once per month for the next 6 months until the first annual follow up.
- (a) The option to continue on a once per month basis for the second year following the initial stimulation will be offered but will not be required.

7) Proposed Claims

- a) Demonstrate the effectiveness of cochlear implantation in children with moderate to profound UHL
 - i) Demonstrate an improvement in speech perception abilities, localization, and/or subjective benefit in an aided (cochlear implant on) versus an unaided (cochlear implant off) condition

- ii) Demonstrate improvement in ability, or improved ease, to participate in natural environments based on parental perception of benefit.

8) Statistical Analysis

- a) Descriptive summaries will be provided for the following: participant demographics, and frequency of major and minor complications/adverse events.

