- b) A single-subject design will be utilized, where each participant serves as his or her own control, for analysis of objective and subjective results. A single-subject design was chosen in order to accommodate the heterogeneity that is well known to characterize auditory prosthesis research. Repeated-measures ANOVA will be calculated with a p-value of ≤ 0.05 for statistical significance. Statistical analysis will be conducted with SPSS software.
 - i) Comparison of aided speech perception performance to the baseline condition (either unaided or aided with hearing aid, depending on the participants residual hearing) and in the post-initial activation intervals to evaluate trends over time
 - ii) Comparison of localization abilities to the baseline condition (either unaided or aided with hearing aid, depending on the participant's residual hearing) and in the post-initial activation intervals to evaluate trends over time
 - iii) Compute the overall rms error, random error, constant error, and adjusted constant error, as described by Grantham et al (2007)
 - iv) Comparison of subjective report scores in the post-initial activation intervals. Group means compared with Bonferroni's adjusted t tests or repeated-measure ANOVAs. Pearson's correlations will be used to analyze relationships between variables.
 - v) Subjective report scores will be compared to norms for this test. Group means compared with Bonferroni's adjusted t tests or repeated-measure ANOVAs. Pearson's correlations will be used to analyze relationships between variables.
- c) The incidence of interference between ears will be assessed at the 6,12 and 24 month post initial stimulation visit by comparing the speech perception performance in the 0° azimuth conditions for the contralateral ear only versus cochlear implant + contralateral ear conditions for each participant, as well as the individual's subjective report.

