A sample size of 20 participants was selected due to known variability in conventional cochlear implant recipient outcomes and to allow for possible dropouts (approximately 20%). A comparable study, Hansen, Gantz & Dunn (2013) evaluated 29 adult cochlear implant participants with UHL, which included etiologies of sudden sensorineural hearing loss, Meniere's disease, and vestibular schwannoma. Authors reported a high degree of variability in their sample. This project will not enroll all of the etiologies included in the Hansen, Gantz & Dunn (2013) analysis (such as, Meniere's Disease with intractable vertigo or history of vestibular schwannoma), therefore a smaller sample size was selected. The inclusion/exclusion criteria associated with this study, as compared to the heterogeneity of the Hansen, Gantz, & Dunn (2013) subject sample, will allow for more generalized comments about subjective and objective outcomes of cochlear implantation in pediatric cases of UHL.

If needed, statistical consultation will be sought from the North Carolina Translational and Clinical Sciences Institute (TraCS) or UNC Odum Institute.

9) Endpoints

- a) Safety endpoint
 - i) The primary safety endpoint is the evaluation of Adverse Events. All Adverse Events will be reported to the UNC IRB. If the UNC IRB or study investigators deem an Adverse Event unacceptable, then this would result in termination of the study.
- b) Primary effectiveness endpoint
 - i) The primary effectiveness endpoint is the comparison of speech perception, localization abilities and/or subjective report when the cochlear implant is on versus the preoperative unaided condition as well as changes in quality of life as measured by the Speech, Spatial and Qualities of Hearing Scale (SSQ), (Gatehouse & Noble 2004), the modified Bern SSD Questionnaire, (Kompis, Pfiffner, Krebs & Caversaccio , 2011) and the PedsQL Multidimensional fatigue scale (Varni, Limbers & Burwinkle, 2007).

10) Risk Analysis

- a) Potential risks to cochlear implantation

The following are risks associated with the MED-EL Synchrony implant, which is included in the device description:

1. Loss of residual hearing
2. Dizziness
3. Increased vertigo
4. Delay of healing of the scar
5. Impairment of the sense of taste

6. Potential for swallowing difficulties
7. Numbness
8. Increased tinnitus
9. Stimulation of the facial nerve
10. Temporary pain and uncomfortable sounds during stimulation

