complete a hearing aid trial prior to enrollment to evaluate outcomes with conventional amplification. If a child has any residual hearing in the ear to be implanted, surgical placement of a cochlear implant will result in a loss of this hearing. The amount of functional gain a hearing aid can afford for a hearing loss with a pure tone average of >70dB HL will be very likely be insufficient to achieve comprehension of spoken language. Current research in performance outcomes for children with cochlear implants suggests that children with a 67dB PTA have a 80% chance of improved hearing with a cochlear implant and children with a 73dB PTA have a 85% chance of improvement with a cochlear implant (Leigh, Dettman & Dowell, 2016). If a child does not benefit from the cochlear implant, or does not elect to use it, this does not preclude him or her from use of a CROS hearing aid or Bone Conduction device in the future. This technology, which uses a contralateral microphone to route sound to the better hearing ear, either by way of short wave radio or bone conduction, can still be used.

- (1) The test battery includes a listening condition to assess the monaural performance of the contralateral ear. Interference of the cochlear implant on the performance of the contralateral ear can be evaluated by comparing the contralateral ear only condition to the cochlear implant + contralateral ear conditions when tested at 0° azimuth. This will be done at the 1 and 2 year test intervals only. Additionally, we will review the subjective benefit via the subjective questionnaires. If interference is found to impact speech perception and subjective benefit, the participant may elect to discontinue use of the cochlear implant and would still have access to currently approved technologies for UHL
 - ii) Magnet strength will be assessed at each interval to ensure comfort at the coil site.
 - iii) Reports of pain from the external speech processor placement will be addressed by different wearing options (i.e. moleskin between the external speech processor and the participant's ear, or different battery-wearing options to lighten weight on the pinna).
 - iv) Mapping will be conducted at each post-initial activation interval to improve audibility and comfort of the sound quality from electric stimulation.
 - v) The MED-EL cochlear implant has MRI limitations*. Participants may have CT scans or x-ray imaging postoperatively when warranted.

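### Claim 7.a.i labels the postoperative implant-off state unaided, so in children with usable residual hearing the on-off difference can include hearing lost to surgery

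*Combined protocol and SAP*

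**What the plan says.** The background states the primary goal as finding out whether children do better "with a cochlear implant as compared to an unaided listening condition". Claim 7.a.i turns this into a contrast "in an aided (cochlear implant on) versus an unaided (cochlear implant off) condition", offered in support of the effectiveness of implantation.

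Section 10.c.i (Risk Mitigation) says that if the child has any residual hearing in the ear, "surgical placement of a cochlear implant will result in a loss of this hearing". Loss of residual hearing is also the first risk listed in section 10.a.

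The inclusion criteria in 6.b.i limit residual hearing but do not exclude it:
- criterion (1)(a): "Unaided residual hearing thresholds that yield a PTA at frequencies 500Hz, 1K Hz and 2K Hz of ≥ 70 dB HL", followed by "It is possible that subjects may have hearing at other frequencies not included in this average";
- criterion (7): "Aided word recognition in the ear to be implanted of 30% or less".

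Other sections name other comparators. The primary effectiveness endpoint (9.b.i) compares outcomes "when the cochlear implant is on versus the preoperative unaided condition". Sections 8.b.i and 8.b.ii compare with a baseline that is "either unaided or aided with hearing aid, depending on the participants residual hearing" (8.b.ii differs only by an apostrophe). Section 11.d mentions preoperative performance and processor on versus off as two alternatives.

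**The concern.** Off and unaided coincide only in a child who had no useful hearing in that ear before surgery. In a child who had some, the operation lowers the off score, and the on-off difference widens without the implant adding anything. A listed harm would then enlarge an efficacy result. Claim 7.a.i is about implantation, which includes the surgery, and not only about switching the processor on. At stake is whether the on-off results for localization and speech in noise may be reported as improvement over unaided hearing.

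**Working it through.** **1. The contrast taken apart.** Take one child and one task, scored so that higher is better (reverse the sign for localization error). Let Pre be the preoperative unaided score, and Off and On the two postoperative scores. Then

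On − Off = (On − Pre) + (Pre − Off).

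This is an identity. The first term is the net gain over the preoperative unaided state. The second is the hearing lost to surgery, provided nothing else moves unaided performance between the two dates. It is zero if the ear contributed nothing before surgery and positive if it helped with the task.

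**2. Can the second term be non-zero in this sample?** Yes, on the entry criteria. The PTA averages 500, 1000 and 2000 Hz only. Thresholds of 30, 80 and 100 dB HL give (30 + 80 + 100)/3 = 70, and 45, 75 and 90 give (45 + 75 + 90)/3 = 70. Both patterns meet criterion (1)(a), although such a child must still meet the word-score limit. Hearing outside the three frequencies has no stated limit. Section 8.b also lets the baseline depend on residual hearing, so the plan expects some children to have it.

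**3. Which outcomes are exposed?** From the readable visit lists in 6.c and the battery in 6.d:

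| Outcome | Listed before surgery | Tested both on and off afterwards |
|---|---|---|
| CNC words in quiet | Yes, unaided and aided | No; given by direct input to the processor |
| BKB-SIN | Not listed | Yes, at 6, 12 and 24 months |
| Localization | Not listed | Yes, at 3, 9, 18 and 24 months |
| Parent questionnaires | Yes | No on/off condition listed |

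The two outcomes with an on-off contrast are the two with no listed preoperative test.

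**4. Size.** The plan gives no effect size, standard deviation or power. Its only related figures are 20 children and about 20% dropout, which leave 20 × (1 − 0.20) = 16. At group level the excess is p × L, where p is the share of children with usable residual hearing and L their mean loss on the task. The documents give neither.

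To show what p × L could do, I make three assumptions: no net gain over the preoperative state; a paired comparison at two-sided 0.05 (for two conditions, repeated-measures ANOVA is equivalent to a paired t-test; the plan does not state sidedness); and an average loss expressed in SDs of the paired on-off difference. An average of 0.2 SD arises, for example, from p = 0.5 and L = 0.4 (0.5 × 0.4 = 0.2). The probability of a significant result in the direction of benefit is P(T > t₀.₉₇₅), with T noncentral t on n − 1 degrees of freedom and noncentrality (average loss) × √n.

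| Average loss (SD, assumed) | n = 16 | n = 20 |
|---|---|---|
| 0 | 2.5% | 2.5% |
| 0.1 | about 6% | about 6% |
| 0.2 | about 11% | about 13% |
| 0.3 | about 20% | about 25% |
| 0.5 | about 46% | about 56% |

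These rows show sensitivity to an unknown. They are not an estimate for this trial.

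**The case against.** The case against is substantial.

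- **The effect may be small.** Entry requires a PTA of at least 70 dB HL in the ear, the localization noise is presented at 70 dB SPL, the other ear hears normally, and section 10.c describes candidates as having little or no useful hearing in the ear. This stands. It limits the size but does not remove the term, because hearing at other frequencies is allowed.
- **The main comparators are preoperative.** A reader might infer that the primary effectiveness result is inflated. The documents do not support that: 9.b.i names the preoperative unaided state, 8.b.i-ii name a baseline, and section 8 specifies no on-off efficacy test. The point is confined to 7.a.i and to results reported under it.
- **A baseline may exist.** A reader might infer that localization and BKB-SIN have no preoperative test at all. That is not established. The opening of 6.d includes a preoperative interval, 8.b.ii presumes a localization baseline, and the Appendix A timeline could not be read. Even with a baseline, the label in 7.a.i would be wrong for these children.
- **The 30% word-score limit is not a measure of the excess.** A reader might infer an overstatement of up to 30 points. That limit is a hearing-aid score, while the term here is unaided. CNC also has no off condition after surgery, so no such on-off difference can arise.
- **On-off has a merit of its own.** Both conditions are tested at the same age, so growth cancels. That matters in children implanted between 3 years 6 months and 6 years 6 months and followed for 24 months, and it is a reason to keep the contrast under an accurate name.

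**Conclusion.** The point holds as a correction to what claim 7.a.i can support. The protocol says that residual hearing in the implanted ear is lost to surgery, admits children who have such hearing, and then labels the postoperative off state as unaided. In those children on-off exceeds the net gain over the preoperative unaided state by the hearing lost. The direction rests on two assumptions: that the residual hearing helped with the task, and that age and practice effects are set aside. The size cannot be derived from the documents. It is zero for children without usable hearing in the ear and may be small for the group. The exposure is to localization and BKB-SIN, for which on-off is the only unaided-type contrast in the readable schedule.

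A reader might go further and allow the claim only in children with no measurable hearing. The documents do not define that group. The restriction would split 16 to 20 children into subsets of unknown size and would leave out children whose thresholds are measurable but of no practical use.

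**What to change.** 1. In 7.a.i, call the control condition *processor off* and drop the word *unaided*.
2. State in sections 7 and 8 that on-off measures the processor's contribution after surgery, not the net effect of implantation.
3. Reserve any statement of improvement over unaided hearing for the comparison in 9.b.i, and only for outcomes with preoperative data. Say explicitly whether localization and BKB-SIN have such data.
4. Show on-off results descriptively, child by child, beside the preoperative unaided thresholds that 6.c already collects. Add the before-to-after threshold change in the implanted ear where it is measured. Section 6.d.i lists air-conduction thresholds in both ears, but the visit lists at 6, 12 and 24 months name only the contralateral ear, so this needs to be made clear.

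The cost is some rewording and one descriptive table, largely from data already planned. The downside is real: if no preoperative localization or BKB-SIN data exist, the study can claim only a processor on-versus-off benefit for those two outcomes.

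### The parent-perception claim and the questionnaire part of the primary endpoint rest on at least seven scores, with no deciding score, no any/all rule and no multiplicity family across scores

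*Combined protocol and SAP*

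**What the plan says.** **The claim.** Section 7) a) ii) proposes to "Demonstrate improvement in ability, or improved ease, to participate in natural environments based on parental perception of benefit". It names no instrument, score, visit or success rule.

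**The instruments.** Section 6) d) vi) describes three parent questionnaires.
- SSQ, modified: "The SSQ questionnaire assesses performance in three domains, hearing speech in quiet and noise environments (9 items), spatial or directional hearing (5 items"), plus a sound-qualities domain of 8 items. On scoring, "Domain scores represent an average of item ratings"; no total is mentioned.
- Bern SSD, modified: "This is a 10-item questionnaire used for rating the subjectively perceived benefit of a hearing technology". Its scoring is not described.
- PedsQL fatigue scale: "including general fatigue, sleep/rest fatigue and cognitive fatigue". No total is mentioned.

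**The endpoint.** Section 9) b) puts all three in the primary effectiveness endpoint: "as well as changes in quality of life as measured by the Speech, Spatial and Qualities of Hearing Scale (SSQ"), followed by the modified Bern and the PedsQL fatigue scale.

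**The analysis.** The general rule in section 8) b) is "Repeated-measures ANOVA will be calculated with a p-value of ≤ 0.05 for statistical significance". For subjective scores, 8) b) iv) (comparison in the post-activation intervals) and 8) b) v) (comparison with norms) both add: "Group means compared with Bonferroni's adjusted t tests or repeated-measure ANOVAs".

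**The visits.** Section 6) c) schedules the questionnaires preoperatively and at 3, 6, 9, 12, 18 and 24 months. Section 5) c) makes 24 months the study endpoint for each participant, but no section names a deciding visit for the questionnaires.

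**The concern.** The scores cover different things: hearing speech, spatial hearing, sound quality and listening effort, perceived device benefit, and three kinds of fatigue. They can disagree. With no deciding score and no any/all rule, the reading of mixed results can be settled after the data are seen.

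The Bonferroni wording does not close the gap. It is one of two alternatives, and the other, a repeated-measures ANOVA for each score, adjusts for nothing across scores. Where Bonferroni is used, the number of comparisons it covers is not given.

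This is a separate matter from the choice among speech perception, localization and subjective report in 9) b). If subjective report were fixed as the deciding domain and the test method settled, seven scores would still sit inside it, and 7) a) ii) would still be a claim of its own.

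**Working it through.** **The plan's own figures.** It states no familywise error rate for the questionnaires, so there is none to reproduce. The sample size of 20 has no effect size, SD or power behind it. With the stated dropout of about 20%, 20 × 0.80 = 16 children are evaluable.

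**Inputs from the documents.** Level 0.05 (8) b)); 3 + 1 + 3 = 7 scores (6) d) vi)); six post-activation visits; n = 16, with 20 as a check.

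**Assumptions.** Two-sided tests, so 0.025 falls in the benefit direction (sidedness is not stated); Bern scored as one total; a common correlation ρ between change scores, not given and varied from 0 to 0.9.

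**Step 1. Independent scores, one visit versus preoperative.**
1 − (1 − 0.025)^7 = 1 − 0.975^7 = 16.2%.
One score: 2.5%. With two time points a repeated-measures ANOVA is the paired t test (F = t²), so this also covers the ANOVA route at a single visit.

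**Step 2. Correlated scores.** Simulate trials with no true effect. For each score compute t = mean change / (SD/√n), and count trials in which at least one t exceeds the 97.5th percentile of t on n − 1 degrees of freedom.

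| ρ | 7 scores, n = 16 | 7 scores, n = 20 |
|---|---|---|
| 0.3 | 13.8% | 14.0% |
| 0.5 | 12.0% | 11.6% |
| 0.7 | 9.3% | 9.3% |
| 0.9 | 6.0% | 5.9% |

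Letting scores correlate more within an instrument (0.6 to 0.7) than between instruments (0.2 to 0.5) gives 10.6% to 12.9%, using normal test statistics.

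**Step 3. One total per questionnaire (three scores).** Independent: 1 − 0.975^3 = 7.3%. For n = 16: 6.3% at ρ = 0.5 and 4.4% at ρ = 0.9.

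**Step 4. Bonferroni across the six visits within each score.** Each test has 0.025/6 in the benefit direction; n = 16, assumed correlation 0.5 between visits. A single score is controlled, at about 2.1%. Seven scores give about 12% to 13% at ρ = 0.3, 11% to 12% at 0.5, and just under 8% at 0.8.

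**Step 5. Bonferroni across the seven scores at one visit.** The threshold is 0.05/7 = 0.00714 two-sided, or 0.025/7 in the benefit direction. The error is at most 7 × 0.025/7 = 2.5%, and about 2.1% at ρ = 0.5 with n = 16.

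**The case against.** **No any-one-score rule is stated.** The word *or* in 7) a) ii) joins two constructs, ability and ease, not seven scores. In 9) b) the three questionnaires are joined by *and*; the *and/or* there concerns speech perception, localization and subjective report. If all seven scores had to be significant, the false-claim rate at ρ = 0.5 would be well under 0.1%. This stands: the inflated figures are conditional. The plan does not state an all-scores rule either, so the permissive reading stays open.

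**Bonferroni is already in the plan.** It appears twice for subjective scores, and a family spanning the seven scores would hold the error at or below 2.5% (step 5). So it would be wrong to say that the plan ignores multiplicity. What remains is that the family is undefined and that the alternative route carries no adjustment across scores. The reading closest to 8) b) iv), adjustment across visits, does not solve the problem (step 4).

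**Stronger readings that a reader might infer.**
- One could count seven scores at six visits as 42 unadjusted t tests and arrive at about 40%. The documents do not support this. Unadjusted visit-by-visit t tests are neither of the options in 8) b) iv): one is Bonferroni-adjusted and the other gives one overall visit test per score.
- One could say that a change in sleep/rest fatigue alone would be reported as meeting the claim. Nothing in the documents says so; they only fail to exclude it.

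**It is a feasibility study of 20 children.** True, and this limits how much formality is reasonable. But section 2) sets out to demonstrate effectiveness, section 7) proposes claims, and section 8) sets a significance level.

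**Parents know that the child is implanted.** That is a source of bias which neither a deciding score nor an adjustment removes. It is not part of this point.

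**Conclusion.** The point holds as a gap in specification with a material, conditional cost. At least seven parent-report scores feed claim 7) a) ii) and the questionnaire part of 9) b), and the plan gives no deciding score, no any/all rule and no multiplicity family across scores.

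If any single score at two-sided 0.05 may support the claim, the false-benefit risk at one visit is roughly 6% to 16%, or about 4% to 7% with one total per questionnaire, against 2.5% for one score. Every correlation tried for the seven scores, up to 0.9, gives more than twice 2.5%. Bonferroni across visits within each score leaves about 8% to 13% for between-score correlations of 0.8 down to 0.3.

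A reader might take 12% as the error rate of the plan. It is not. It rests on an assumed correlation of 0.5, 16 evaluable children, two-sided tests, no adjustment across scores and the any-one-score reading, none of which is fixed by the documents except the approximate number of children. The change should be made before the questionnaire data are analysed.

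**What to change.** Amend 7) a) ii), 8) b) and 9) b) in one of two ways.

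1. **One deciding score.** Name one parent-report score, 24 months versus preoperative, with a paired test at two-sided 0.05. Twenty-four months is already the study endpoint in 5) c). The mean of the three modified SSQ domain scores is one possibility. The plan does not define that composite or rank SSQ above Bern, so the choice is the sponsor's. Report the other scores as supportive with Holm-adjusted p values, and state that they do not establish the claim alone.
2. **One family.** Keep all seven scores and define the Holm or Bonferroni family as all seven at 24 months versus preoperative. State that Bern is scored as one total, or recount the family. With the Bonferroni threshold of 0.05/7 the error in the benefit direction is at most 2.5%.

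In either case, say what role the repeated-measures ANOVA over visits plays, for example description of trends.

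**Cost.** Wording only; no new data or visits. The downside is small: an effect confined to one subscale becomes supportive evidence (option 1) or must meet a stricter threshold (option 2).
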